6.3 Selection of Study Population

6.3.1 Inclusion Criteria

For inclusion into the trial, subjects are required to fulfill all of the following criteria:

1. Male or female of any age; however, if female:
 - must be using contraception if of childbearing potential or must be surgically sterile
 - must not be lactating
2. Diagnosis of Type 3 GD by enzyme and sequence analysis; and confirmed by the Medical Monitor.
3. Splenomegaly at least 5 x multiples of normal (MN).
4. Treatment-naïve.

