6.3.3 Removal of Subjects from Study

Reasons for permanent discontinuation include the following:

1. The subject experiences two or more Grade 3 toxicities or one or more Grade 4 toxicity considered by the Investigator associated with taliglucerase alfa treatment (see [Section 8.2.1: Adverse Events](#); and [Appendix 14.5: WHO Common Toxicity Criteria](#))
2. The subject experiences progressive hypersensitivity or severe hypersensitivity will be treated appropriately and may be withdrawn from the study, at the discretion of the treating Investigator and/or Medical Monitor (see [Appendix 14.2: Infusion Rate Algorithm](#); and [Appendix 14.3: Taliglucerase Alfa Hypersensitivity Evaluation and Treatment Algorithm](#))
3. The subject, or subject's parent or guardian, requests to discontinue treatment
4. Investigator feels that it is not in the best interest of the subject to continue treatment and/or the Investigator believes that the subject can no longer be compliant with the requirements of the study
5. Deteriorating clinical condition, which the Investigator decides additional treatments would be needed

For any discontinuation, the Investigator will obtain all required details and document the date and the main reason for the premature discontinuation. If the reason for discontinuation is an adverse event, the specific event or the main laboratory abnormality will be recorded in the case report form (CRF). The Investigator will make thorough efforts to document the outcome. The Investigator will attempt to continue to follow the subject for the full duration of the study or at least for 30 days following discontinuation. If circumstances prevent the subject from completing all visits, every attempt will be made to complete all procedures listed in [Section 9.2.11](#) for Visit 27.

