6.3.4 Replacement Policy

Withdrawn subjects will not be replaced.

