10.1 Determination of Sample Size

It is assumed that the Type 3 GD patients and Type 1 GD patients will have similar efficacy response to taliglucerase alfa 60 units/kg. Given the fact that Type 3 GD usually develops at younger age and 60 units/kg is the recommended dose, data from the 5 treatment-naïve pediatric patients (Type 1 GD) treated with taliglucerase alfa 60 units/kg in Study PB-06-005 are used to calculate sample size. Since the available data are limited and the data distribution is unknown, a responder rate is calculated from the percent change from baseline in spleen volume MN in these 5 patients as a reference. A subject is considered a responder if the subject has a reduction from baseline in spleen volume MN greater than 20%.

The sample size and power calculation are then estimated using the exact computation from a 2-sided sign test for the null hypothesis that the responder rate is equal to 0.5 for this single-group design. This null hypothesis is corresponding to a median reduction of 20% in spleen volume at Month 12. A sample size of 9 evaluable subjects will provide a power of 80.9% to detect a responder rate of 0.91 with an actual significant level of 0.04. An actual significant level of 0.05 is not available when the data are discrete and the sample size is small.

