14.3 Appendix 3: Taliglucerase Alfa Hypersensitivity Evaluation and Treatment Algorithm

During and after infusion of taliglucerase alfa, the following algorithm will be followed to monitor and manage the occurrence of hypersensitivity, anaphylaxis, or anaphylactoid reactions.

Clinical Signs

Early

- Sensations of warmth and itching
- Feelings of anxiety or panic

Moderate

- Pruritus
- Flushing
- Urticaria
- Chest discomfort
- Mild hypotension

Progressive

- Erythematous or massive urticarial rash
- Edema of face, neck, soft tissues

Severe

- Hypotension
- Bronchospasm (wheezing)
- Laryngeal edema (dyspnea, stridor, aphonia, drooling)
- Arrhythmias

Treatment Algorithm

With the onset of any of the above clinical signs, immediately discontinue study medication administration and initiate the following monitoring:

- Continuous electrocardiographic monitoring
- Continuous pulse oximetry
- Measure blood pressure every 5 minutes
- Perform chest auscultation every 5 minutes

- Blood samples need to be collected for Tryptase (29-33) and antibodies. Tryptase samples need to be withdrawn at:
 - 1st sample taken 0.25-3 hours after onset of symptoms
 - 2nd sample taken between 3-6 hours
 - 3rd sample taken 24-48 hours to verify the return to baseline

In the case of progressive or severe hypersensitivity, treat appropriately and withdraw the subject from the study. Treat as detailed below.

Urticaria or edema of the face, neck, or soft tissues

- Epinephrine 1:1000 solution, 0.5 mL subcutaneously, repeat as needed every 5-10 minutes
- Antihistamines
- Corticosteroids

Hypotension (systolic blood pressure (SBP) \leq 90 mmHg)

- Isotonic sodium chloride solution, 1 L every 30 minutes as needed to maintain SBP >90 mmHg
- Epinephrine 1:10,000 solution given IV at 1 μ g/minute initially, then 2-10 μ g/minute to maintain SBP >90 mmHg
- Norepinephrine 4 mg in 1 L 5% dextrose in water given IV at 2-12 μ g/minute to maintain SBP >90 mmHg
- Glucagon 1 mg in 1 L 5% dextrose in water given IV at 5-15 μ g/minute for refractory hypotension

Bronchospasm

- Oxygen by face mask at 6-8 L/minute to maintain oxygen saturation at $>90\%$
- Epinephrine 1:1000 solution, 0.5 mL subcutaneously
- Albuterol 0.5 mL of 0.5% solution in 2.5 mL of sterile saline every 15 minutes up to three doses
- Inhaled beta-agonists
- Corticosteroids

Laryngeal edema

- Epinephrine 1:1000 solution, 0.5 mL subcutaneously, repeat as needed every 5 to 10 minutes
- Corticosteroids

Premedication

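### Appendix 14.3 fixes rescue amounts and a blood-pressure threshold that do not vary with age or weight in a trial open to any age, and its withdrawal rule conflicts with Section 6.3.3

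*Protocol*

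**What the plan says.** Protocol Appendix 14.3 introduces its instructions as binding: "the following algorithm will be followed to monitor and manage the occurrence of hypersensitivity, anaphylaxis, or anaphylactoid reactions". It then lists treatment under four headings.

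- **Urticaria or edema:** "Epinephrine 1:1000 solution, 0.5 mL subcutaneously, repeat as needed every 5-10 minutes". The same 0.5 mL of 1:1000 also appears under bronchospasm and laryngeal edema, so under three of the four headings.
- **Bronchospasm:** in addition, albuterol 0.5 mL of a 0.5% solution every 15 minutes, to a maximum of three doses.
- **Hypotension:** defined as systolic pressure of 90 mmHg or below. Fluid is "Isotonic sodium chloride solution, 1 L every 30 minutes as needed to maintain SBP >90 mmHg". Intravenous epinephrine (1, then 2 to 10 µg/min), norepinephrine (2 to 12 µg/min) and glucagon (5 to 15 µg/min) are absolute rates.

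Neither these lists nor the premedication text after them mentions age, children or dose per kilogram.

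The population is "Male or female of any age" (6.3.1), with no weight floor, and Section 10.1 notes that "Type 3 GD usually develops at younger age".

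On stopping, Appendix 14.3 says: "In the case of progressive or severe hypersensitivity, treat appropriately and withdraw the subject from the study". Section 6.3.3 item 2 says that such a subject "may be withdrawn from the study, at the discretion of the treating Investigator and/or Medical Monitor", and the synopsis agrees. Appendix 14.2 is also permissive for severe reactions.

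**The concern.** An emergency instruction is read under time pressure. A site that follows Appendix 14.3 to the letter gives a small child the same epinephrine and albuterol doses as an adult. It orders fluid and vasopressors in the same absolute amounts, and starts and stops treatment for hypotension at the same systolic figure. If those amounts or that figure do not suit a young child, the protocol itself directs the error.

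The withdrawal wording is a separate matter. Section 6.3.3 item 2 makes withdrawal discretionary and cites Appendix 14.3, where the reader finds an order. Two sites could each follow the protocol and handle the same reaction differently.

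**Working it through.** The plan states no figure on this point, so there is none to reproduce. The check compares the texts and then converts the amounts to a per-kilogram scale.

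**1. Does any other text supply a pediatric rescue rule?**

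- Section 9.2.3 lets procedures depend on local standards of care. It covers Visits 2 to 5 only, not Visit 1 (the first exposure) or Visits 6 to 27, and gives no rescue amounts.
- Section 7.9 lists rescue drugs as permitted, without doses.
- Appendix 14.4.3.2 lets sites use institutional protocols for pediatric MRI sedation.
- Label sections 2.2 and 2.3 (Appendix 14.1) give pediatric volumes and rates for the study drug.

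The last two show that children are treated separately elsewhere. None of the four covers emergency treatment of a child.

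**2. Amounts per kilogram.** The weights come from label section 12.3, Table 3, 60 units/kg columns: pediatric minimum 16.5, median 28.6 and maximum 50.4 kg (n = 4); adult median 73.5 kg. A 1:1000 solution is 1 mg/mL, so 0.5 mL is 0.5 mg. Each entry is amount ÷ weight.

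| Order | 16.5 kg | 28.6 kg | 50.4 kg | 73.5 kg |
|---|---|---|---|---|
| SC epinephrine, 0.5 mg (mg/kg per dose) | 0.0303 | 0.0175 | 0.0099 | 0.0068 |
| Saline, if a full 1,000 mL is needed (mL/kg) | 60.6 | 35.0 | 19.8 | 13.6 |
| IV epinephrine start, 1 µg/min (µg/kg/min) | 0.0606 | 0.0350 | 0.0198 | 0.0136 |
| Weight ratio to 73.5 kg | 4.45 | 2.57 | 1.46 | 1 |

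The rows are one fact, the weight ratio, and it applies equally to albuterol, norepinephrine and glucagon. The inclusion criteria also allow smaller children. At an assumed 10 kg, the epinephrine dose is 0.5 ÷ 10 = 0.05 mg/kg and the ratio is 73.5 ÷ 10 = 7.35.

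**3. How often might rescue be needed?** The label's safety data cover 32 + 26 = 58 adults and 9 + 5 = 14 children, 72 in all. Label 5.1 reports two patients with signs of anaphylaxis. Label 6.2 places two who met anaphylaxis criteria among treatment-naïve adults, and I take these to be the same two. Exact (Clopper-Pearson) 95% limits are:

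- Anaphylaxis, adults, 2/58: 0.4% to 11.9%.
- Anaphylaxis, children, 0/14: upper limit 1 − 0.025^(1/14) = 23.2%.
- Any hypersensitivity reaction, treatment-naïve children, 2/9: 2.8% to 60.0%. Both responded to antihistamines and continued (label 6.1).

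**4. How far does the withdrawal conflict reach?** Section 6.3.3 item 1 makes one Grade 4 toxicity, or two or more Grade 3 toxicities, judged associated with treatment a reason for permanent discontinuation. In Appendix 14.5, Grade 4 allergy is anaphylaxis, so for drug-associated anaphylaxis 6.3.3 and 14.3 agree. They differ below that level. A single bronchospasm needing parenteral medication is Grade 3 allergy in 14.5 and a severe sign in 14.3: 14.3 orders withdrawal, while 6.3.3 item 2 leaves it to judgment.

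**The case against.** The strongest reply is that clinicians keep latitude. Saline is given as needed, the intravenous epinephrine and norepinephrine rates are ranges adjusted to pressure, and the appendix asks for appropriate treatment. The label ties management to severity. This stands in part: no clinician is forced to run a full litre or the top of a range. But the appendix follows its call for appropriate treatment with an instruction to use the listed measures, the epinephrine and albuterol doses are fixed, and nothing substitutes a pediatric amount or threshold.

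A second reply is that need in children looks low. None of 14 had reported anaphylaxis, the two reacting treatment-naïve children continued treatment, and exclusion criterion 13 removes people with a history of food or drug allergy. This also stands. With 14 children it does not exclude the event.

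A reader might infer more than the documents support, in three ways:

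- **That children would be overdosed.** A weight ratio shows that the order is unscaled, not that it is harmful. The documents contain no pediatric dose limits or blood-pressure norms.
- **That the withdrawal conflict endangers the nine completers**, since "Withdrawn subjects will not be replaced". Up to 15 subjects are enrolled to yield nine. Section 6.3.3 asks for continued follow-up and Visit 27 procedures after discontinuation. SAP 5.3 keeps early leavers in the primary analysis through early-termination MRI, then ultrasound, then the baseline value.
- **That the discretionary wording is the right one.** It would relax the stricter rule, and it would not by itself make sites act alike. The documents do not settle the direction.

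**Conclusion.** The point holds as a patient-safety gap in one appendix and a narrower inconsistency in the stopping rule.

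Appendix 14.3 is mandatory and unscaled in a trial that expects children, and no other section gives a pediatric rescue rule. Per kilogram, the same order is about 1.5 to 4.5 times the adult amount over the label's pediatric weight range. Those weights come from four Type 1 patients; this trial's age and weight mix is not stated. That the amounts, or a systolic figure of 90 mmHg, are unsuitable for a young child is an assumption. A child needing the rescue steps is neither shown to be likely nor ruled out.

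The withdrawal conflict is real for progressive or severe reactions that do not already meet 6.3.3 item 1. It does not extend to anaphylaxis judged associated with treatment, and no effect on the trial's power is shown. The case for acting rests on the possible seriousness of an error and the low cost of preventing it.

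**What to change.** **Rescue treatment.** State in Appendix 14.3 that pediatric subjects are treated under the site's pediatric emergency procedure. Alternatively, give age- and weight-based amounts and an age-appropriate definition of hypotension, set by the sponsor's clinicians. No dose or threshold is proposed here. Because Section 6.1 allows home infusion at some centers, the text should also say what applies there.

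**Withdrawal.** The sponsor should choose one rule for progressive or severe hypersensitivity, mandatory or discretionary, and use it in Appendix 14.3, Section 6.3.3 item 2, the synopsis and Appendix 14.2. It must be consistent with 6.3.3 item 1, so that Grade 4 anaphylaxis associated with treatment remains a reason to discontinue.

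**Cost.** Amendment text, mainly in one appendix, and site re-training. No added visits, assessments or subjects.

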14.4 Appendix 4: Magnetic Resonance Imaging (MRI)

14.4.1 Subject and Sites

Nine subjects will be enrolled in this study by 5 to 10 sites worldwide.

14.4.2 MRI Data

Each subject enrolled in this study will have 2 MRI time points during the course of the trial at Baseline and Month 12 (or early termination). For each time point, the same set of T1 and T2-weighted MRI sequences will be acquired. An imaging manual will be shared with sites to outline the scanning protocol. The exact sequence parameters will be defined based on site's equipment and abilities to provide sufficient image quality and contrast for organ (spleen and liver) detection and quantification, and full spleen and liver coverage in GD subjects. No contrast agent will be used.

An MRI of the abdomen containing the entire spleen and liver will be collected at the Screening visit (Day -25 ± 10) and Week 52 Visit (± 7 days). Volumes of liver and spleen will be evaluated centrally by an independent radiologist. All scans should be submitted within 2 days of acquisition to allow quality review by the central radiologist. The MRI site must confirm the scan is acceptable prior to sending images for central review. The inspection by the site will include complete anatomic coverage of the liver and spleen. Scans that are not accepted by the central radiologist may result in rescan requests. The method of evaluation used for each patient at baseline should remain consistent for the duration of the study. In instances when the scan must be repeated (ie, if upon submission to the central radiologist, quality control issues are identified and communicated to the site) the repeated scan must be evaluated.

14.4.3 MRI Evaluation Parameters

The following MRI parameters will be evaluated during this study:

- Volume of spleen (in cm^3)
- Volume of liver (in cm^3)

14.4.3.1 Standardization of Image Acquisition, Initial Site Qualification

The image acquisition procedure will be provided to sites in a separate image acquisition manual. The same image acquisition and management procedure will be used by all sites. All images will be anonymized by the sites (in order to remove any subject-related nominative information) and provided in digital format (DICOM). Only digital images will be centrally processed by the central radiologist.

14.4.3.2 Subject Sedation

Pediatric subjects may require sedation in order to obtain the high quality images required. Sites may use standard sedation protocols approved by the institution.

14.4.3.3 Quality Control of Image Data and Site Quality Assurance During the Course of the Study

The image data will be collected and quality inspected by the central radiologist for checking the technical adequacy, the compliance of data acquisition with the imaging guidelines and the

diagnostic quality of the images (their appropriateness for centralized evaluations). If any quality-related issue is detected by the central reviewer this will be communicated to the site.

14.5 Appendix 5: WHO Common Toxicity Criteria

Category	Toxicity	Grade 0	Grade 1	Grade 2	Grade 3	Grade 4
Hematology	WBC (x10 ³ /L)	4	3.0 - 3.9	2.0 - 2.9	1.0 - 1.9	< 1.0
Hematology	Platelets (x10 ³ /L)	WNL	75.0 - normal	50.0 - 74.9	25.0 - 49.9	< 25.0
Hematology	Hemoglobin (g/dL)	WNL	10.0 - normal	8.0 - 9.9	6.5 - 7.9	< 6.5
Hematology	Granulocytes/ Bands	2	1.5 - 1.9	1.0 - 1.4	0.5 - 0.9	< 0.5
Hematology	Lymphocytes (x10 ³ /L)	2	1.5 - 1.9	1.0 - 1.4	0.5 - 0.9	< 0.5
Hematology	Hemorrhage	none	mild, no	gross, 1 - 2 units transfusion per episode	gross, 3 - 4 units transfusion per episode	massive, > 4 units transfusion per episode
Coagulation	Fibrinogen	WNL	0.99 - 0.75 x N	0.74 - 0.50 x N	0.49 - 0.25 x N	< 0.25 x N
Coagulation	Prothrombin time(Quick)	WNL	1.01 - 1.25 x N	1.26 - 1.50 x N	1.51 - 2.00 x N	> 2.00 x N
Coagulation	Partial thrombo- plastin time	WNL	1.01 - 1.66 x N	1.67 - 2.33 x N	2.34 - 3.00 x N	> 3.00 x N
Metabolic	Hyperglycemia (mg/dL)	< 116	116 - 160	161 - 250	251 - 500	> 500 or ketoacidosis
Metabolic	Hypoglycemia (mg/dL)	> 64	55 - 64	40 - 54	30 - 39	< 30
Metabolic	Amylase	WNL	< 1.5 x N	1.5 - 2.0 x N	2.1 - 5.0 N	> 5.0 x N
Metabolic	Hypercalcemia (mg/dL)	< 10.6	10.6 - 11.5	11.6 - 12.5	12.6 - 13.4	13.5
Metabolic	Hypocalcemia (mg/dL)	> 8.4	8.4 - 7.8	7.7 - 7.0	6.9 - 6.1	6
Metabolic	Hypomagnesemia (mg/dK)	> 1.4	1.4 - 1.2	1.1 - 0.9	0.8 - 0.6	0.5

Category	Toxicity	Grade 0	Grade 1	Grade 2	Grade 3	Grade 4
Gastrointestinal	Nausea	none	able to eat reasonable intake	intake significantly decreased but can eat	no significant intake	-----
Gastrointestinal	Vomiting	none	1 episode in 24 hrs	2 - 5 episodes in 24 hrs	6 - 10 episodes in 24 hrs	> 10 episodes in 24 hrs or requiring parenteral support
Gastrointestinal	Diarrhea	none	increase of 2 - 3 stools / day over pre-Rx	increase of 4 - 6 stools / day, or nocturnal stools, or moderate cramping	increase of 7 - 9 stools / day, or incontinence, or severe cramping	increase of > 10 stools / day or grossly bloody diarrhea, or need for parenteral support
Gastrointestinal	Stomatitis	none	painless ulcers, erythema, or mild soreness	painful erythema, edema, or ulcers but can eat solids	painful erythema, edema, or ulcers and cannot eat solids	requires parenteral or enteral support for alimentation
Liver	Bilirubin (N = 17 μ mol/L)	WNL	-----	< 1.5 x N	1.5 - 3.0 x N	> 3.0 x N
Liver	Transaminase (SGOT, SGPT)	WNL	2.5 x N	2.6 - 5.0 x N	5.1 - 20.0 x N	> 20.0 x N
Liver	Alk phos or 5 nucleotidase	WNL	< 2.5 x N	2.6 - 5.0 x N	5.1 - 20.0 x N	> 20.0 x N
Liver	Liver- clinical	No change from baseline	-----	-----	precoma	hepatic coma
Kidney, bladder	Creatinine	WNL	< 1.5 x N	1.5 - 3.0 x N	3.1 - 6.0 x N	> 6.0 x N
Kidney, bladder	Proteinuria	No change	1 (+) or < 0.3 g% or 3 g/L	2 - 3 (+) or 0.3 - 1.0 g% or 3 - 10 g/L	4 (+) or > 1.0 g% or > 10g/L	nephrotic syndrome
Kidney, bladder	Hematuria	Negative	microscopic only	gross, no clots no Rx needed	gross and clots bladder irrigation	requires trans fusion or cystectomy
Kidney, bladder	Weight gain/ loss	< 5.0 %	5.0 - 9.9 %	10.0 - 19.9 %	20.00%	-----
Pulmonary	Pulmonary	none or no change	asymptomatic, with abnormality in PFTs	dyspnea on significant exertion	dyspnea at normal level of activity	dyspnea at rest

Category	Toxicity	Grade 0	Grade1	Grade2	Grade3	Grade4
Cardiac	Cardiac arrhythmias	none	asymptomatic, transient, requiring no therapy	recurrent or persistent, no therapy required	requires treatment	requires monitoring; or hypotension, or ventricular tachycardia or fibrillation
Cardiac	Cardiac function	none	asymptomatic, decline of resting ejection fraction by less than 20 % of baseline value	asymptomatic, decline of resting ejection fraction by more than 20 % of baseline value	mild CHF, responsive to therapy	severe or refractory CHF
Cardiac	Cardiac ischemia	none	non-specific T- wave flattening	asymptomatic, ST and T wave changes suggesting ischemia	angina without evidence of infarction	acute myocardial infarction
Cardiac	Cardiac-pericardial	none	asymptomatic effusion, no intervention required	pericarditis (rub, chest pain, ECG changes)	symptomatic effusion; drainage required	tamponade; drainage urgently required
Cardiac	Hypertension	none or no change	asymptomatic, transient increase by greater than 20 mm Hg (D) or to > 150 / 100 if previously WNL. No treatment required.	recurrent or persistent increase by greater than 20 mm HG (D) or to > 150 / 100 if previously WNL. No treatment required.	requires therapy	hypertensive crisis
Cardiac	Hypotension	none or no change	changes requiring no therapy (including transient orthostatic hypotension)	requires fluid replacement or other therapy but not hospitalization	requires therapy and hospitalization; resolves within 48 hours of stopping the agent	requires therapy and hospitalization for > 48 hrs after stopping the agent
Neurologic	Neuro: sensory	none or no change	mild paresthesia; loss of deep tendon reflexes	mild or moderate objective sensory loss moderate paresthesia	severe objective sensory loss or paresthesia that interfere with function	-----
Neurologic	Neuro: motor	none or no change	subjective weakness; no objective findings	mild objective weakness without significant impairment of function	objective weakness with impairment of function	paralysis

Category	Toxicity	Grade 0	Grade 1	Grade 2	Grade 3	Grade 4
Neurologic	Neuro: cortical	none	mild somnolence or agitation	moderate somnolence or agitation	severe somnolence, (>50% waking hours), agitation, confusion, disorientation or hallucinations	coma, seizures, toxic psychosis
Neurologic	Neuro: cerebellar	none	slight incoordination, dysdiadochokinesia	intention tremor, dysmetria, slurred speech, nystagmus	locomotor ataxia	cerebellar necrosis
Neurologic	Neuro: mood	no change	mild anxiety or depression	moderate anxiety or depression	severe anxiety or depression	suicidal ideation
Neurologic	Neuro: headache	none	mild	moderate or severe but transient	unrelenting and severe	-----
Neurologic	Neuro: constipation	none or no change	mild	moderate	severe	ileus > 96 hrs
Neurologic	Neuro: hearing	none or no change	asymptomatic, hearing loss on audiometry only	tinnitus	hearing loss interfering with function but correctable with hearing aid	deafness not correctable
Neurologic	Neuro: vision	none or no change	-----	-----	symptomatic subtotal loss of vision	blindness
Pain	Pain	none	mild	moderate	severe	requires narcotics
Skin	Skin	none or no change	scattered macular or papular eruption or erythema that is asymptomatic	scattered macular or papular eruption or erythema with pruritus or other associated symptoms	generalized symptomatic macular, papular or vesicular eruption	exfoliative dermatitis or ulcerating dermatitis
Alopecia	Alopecia	no loss	mild hair loss	pronounced or total hair loss	-----	-----

Category	Toxicity	Grade 0	Grade 1	Grade 2	Grade 3	Grade 4
Allergy	Allergy	none	transient rash, drug fever < 38°C (100.4°F)	urticaria, drug fever 38°C (100.4°F), mild bronchospasm	serum sickness, bronchospasm requiring parenteral medication	anaphylaxis
Local	Local	none	pain	pain and swelling with inflammation or phlebitis	ulceration	plastic surgery indicated
Fever of unknown origin	Fever of unknown origin	none	37.1 - 38.0°C 98.7° - 100.4°F	38.1 - 40.0°C 100.5 - 104°F	> 40.0°C > 104.0°F for less than 24hrs	> 40.0°C (>104°F) for more than 24 hrs or accompanied by hypotension
Infection	Infection	none	mild	moderate	severe	life-threatening
Additional events	Asthenia	analogous to Karnofsky index (WHO grading)				
Additional events	Chills	Analogous to fever				
Additional events	Peripheral edema	analogous to weight gain				
Additional events	Anorexia	analogous to weight loss
